## II. SPECIFIC AIMS

This is the third study in a series of 3 studies to develop a smartphone app to support nondaily smokers in quitting smoking, as funded by the American Cancer Society grant #RSG CPPB – 130323 (project dates: 07/01/2017 – 6/30/2021). Study 1 (2017P001106) demonstrated feasibility and acceptability when smokers were onboarded in person. Study 2 (2018P002699) demonstrated feasibility and acceptability when smokers were onboarded remotely, nationwide. The present study is Study 3. It is a 3-group proof-of-concept RCT, in which we seek to test if our app (i.e., Version 3 of our developed smartphone app, called ‘Smiling instead of Smoking’ (SiS)) is superior to treatment as usual (i.e., TAU; no treatment for nondaily smokers) and superior to a control app (i.e., the National Cancer Institute’s smartphone app “QuitGuide” (QG). Specifically, our aims are to:

1. Test for differences between randomized groups on the primary outcome of this proof-of-concept RCT, as measured at end of treatment (i.e., Week 6 post-quit): Self-efficacy to remain abstinent, as measured via the Smoking Self-Efficacy Questionnaire (SEQ): two-dimensional 12-item self-report scale measuring a person’s confidence in his or her ability to abstain from smoking when facing internal stimuli [e.g. feeling depressed] and external stimuli [e.g. being with smokers]. Participants rate each item on a sliding scale from 0 [not at all confident] to 100 [extremely confident]. Two subscale scores are created by averaging items assessing internal vs. external stimuli, respectively. We hypothesize that SiS > QG > TAU.
2. Test for differences between randomized groups on secondary outcomes:
  - a. Self-reported 30-day point-prevalence abstinence 6, 12 and 24 weeks post quit. We hypothesize that SiS > QG > TAU.
  - b. Self-reported past week cigarette reduction at 2, 6, 12, and 24 weeks post quit, compared to baseline. We hypothesize that SiS > QG > TAU.
  - c. Satisfaction with smoking cessation support, as self-rated on the Client Satisfaction Questionnaire (CSQ-8) at end of treatment. We hypothesize that SiS > QG > TAU.
  - d. Time spent applying content brought up by the apps/”Clearing the Air” at end of treatment (“During this past week, how much time did you spend applying or contemplating the content of the SiS app/QG app/”Clearing the Air”?” [in minutes]). We hypothesize that SiS > QG > TAU.

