(please see attached for the specific check items), staff will inform the screening participant that they are ineligible for the study. If the survey is complete and valid, staff will collect (via email, phone, and/or REDCap form) the contact information for collaterals the participant would like to specify for this study. Social security number (to enable payment by check) and a mailing address to which Accounts Payable can mail the check containing remuneration will be collected via phone, and only after participants have been enrolled in the study. For screen participants who do not enroll in the study (i.e., because they are ineligible or because they decide against the study) study staff will ask for verbal consent (via phone) to allow us to collect their SSN (during the same phone call) and send them a check for completing the screening survey.

At the end of this phone call, study staff will ask the screening participant to indicate the date on which they would like to quit smoking. The enrollment call is then scheduled to occur 8 days before that date. If the chosen quit date falls on a Monday or Sunday, meaning that the enrollment call should be on a Saturday or a Sunday, the enrollment call will be adjusted to fall on a weekday.

During the enrollment call, staff will review the study fact sheet with the participant, and will invite the participant to ask any questions they may have about the study and all its procedures. Once all questions have been answered, study staff will ask the participant to give verbal consent to enroll in this study. The date and time of this verbal consent will be documented by study staff in our REDCap dataset.

After providing verbal consent, the participant is randomized. This is an unblinded study. Randomization will occur via a randomization sheet, as generated using the PROC PLAN procedure in the statistical software package SAS. Randomization will be in a 1:1:1 ratio (SiS3 vs. QG vs. TAU), with a block size of 4. Study staff will use the randomization sheet to determine the participant's treatment group, document this randomized assignment in our REDCap dataset, and will then onboard the participant to the smoking cessation support they have been randomized to receive (i.e., our smartphone app SiS or NCI's app QuitGuide or TAU, which consists of NCI's written materials, "Clearing the Air"), using a time-matched, ~15 minute script.

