We will stop enrollment when n=225 participants have been successfully onboarded to their randomized condition. Based on our experience in Study 1 (#2017P001106) and Study 2 (#2018P002699), we expect that 1/3 of participants who start the screening survey will enroll in the study. Thus, we are estimating that n=675 will be necessary to start the screening survey in order for n=225 to be successfully enrolled to their randomized treatment condition.

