## **V. STUDY PRODECURES**

This is a single site study. Participation will last 6 months (see Figure 2), and entails:

- Completing a scripted onboarding call (approximately 30-45 minutes)
- Making a quit attempt
- Engaging with smoking cessation support (randomized) over the course of seven weeks, one week prior and 6 weeks following the originally chosen quit day

- Completing five online, REDCap-administered surveys, administered prior to the quit day (online, as part of a screening test), and at 2-week, 6-week, 3-month, and 6-month follow-ups of the participant's chosen quit day

[figure not shown]
[figure not shown]

Figure 2. Timeline of study participation

After onboarding, participants will be asked to engage with the smoking cessation materials they receive as part of this study (i.e., smartphone apps or written materials) for a period of seven weeks (1 week before, 6 weeks following the quit attempt). They may choose to continue to use these materials thereafter.

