## **Control Condition #2: Treatment as Usual (TAU)**

Participants in the treatment as usual (TAU) condition will be asked to make a naturalistic quit attempt, using any methods they feel might help them. To time-match the onboarding experience of SiS and QG participants, study staff will use an onboarding script to lead TAU participants through the NCI booklet “Clearing the Air”, which encourages activities in the same order as implemented in the SiS behavioral challenges (i.e., reflecting on reasons to quit, informing about benefits of quitting, logging smoking and its triggers, formulating strategies for dealing with triggers). Additionally, “Clearing the Air” provides information on smoking cessation support resources, such as counseling and pharmacological approaches.

At the end of treatment, participants complete an online survey via REDCap. This is our primary study endpoint (see Specific Aims). Participants complete two more online surveys via REDCap, occurring 12 and 24 weeks post-quit, for secondary aims.

Table 1 specifies which data are collected at which time points. Please see attached for specific descriptions of each of these measures.

Table 1. Data Collection Instruments per Time Point

Type of Measure Specific Measure	Timing of Assessment				
	BL	Wk 2	Wk 6	Wk 12	Wk 24
Primary Outcome					
Smoking Self-Efficacy Questionnaire (SEQ-12)	X	X	X	X	X
Secondary outcomes					
Smoking status	X	X	X	X	X
Recent cigarette use	X	X	X	X	X
Client Satisfaction Questionnaire (CSQ-8)			X		
Time spent applying content			X	X	X
Use of smoking cessation strategies			X		
Perceived impact of SiS/QG/TAU on quitting			X		
Appreciation Scale (AS)			X		
(SiS/QG only) Actual app usage - continuously recorded	X	X	X	X	X
(SiS/QG only) Self-reported app usage: weeks -1 to 2		X			
(SiS/QG only) Self-reported app usage: weeks 3 to 6			X		
(SiS/QG only) App likeability & satisfaction			X		
(SiS/QG only) System Usability Scale (SUS)			X		
Other outcomes to be explored in mediational analyses					
Emotional well-being					
PANAS Positive And Negative Affect Schedule (PANAS)	X	X	X	X	X
Happiness single-item measures	X	X	X	X	X
Satisfaction With Life Scale (SWLS)	X	X	X	X	X
Subjective Happiness Scale (SHS)	X	X	X	X	X
Perceived Stress Scale (PSS10)	X	X	X	X	X
Desire to smoke					
Brief Questionnaire of Smoking Urges (QSU)	X	X	X	X	X
Thought action repertoire					
Modified Twenty Statement Test (mTST) - Baseline	X				

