**Analytic Plan.** All successfully enrolled participants (i.e., passed the screening process, was successfully onboarded to the assigned smoking cessation materials) will be included in the outcome analyses. For hypotheses only relevant to the SiS and QG conditions (marked in Specific Aims), only participants successfully onboarded to those conditions will be included in the analyses.

1. **Primary Outcome (Aim 1).** In this proof-of-concept RCT, the primary outcome is self-efficacy to abstain from smoking, as measured by the SEQ-12. The primary endpoint is end-of-treatment, which occurs 6 weeks after the originally chosen quit day. To test for differences between randomized groups, we will fit a fixed effects repeated measures model using PROC MIXED, where observations are modeled as nested within persons. Predictors included in the model will be GROUP (i.e., SiS vs. QG vs. TAU), TIME (i.e., BL, Week 2, Week 6, Week 12 and Week 24), and the GROUP\*TIME interaction effect. A contrast statement will be used to derive the test statistic for the GROUP comparison at Week 6, our primary endpoint, given the overall longitudinal model. This contrast statement will test the null hypothesis that SiS = QG = TAU. If this null hypothesis is rejected ( $p<0.05$ ), we will conduct pair-wise follow-up tests that compare the three possible pairwise comparisons (i.e., SiS vs. QG, SiS vs. TAU, and QG vs. TAU).
2. **Secondary Outcomes (Aim 2).** The secondary outcomes in this proof-of-concept RCT are exploratory. Thus, we will not correct for multiple testing. We will fit one model per secondary outcome, using an alpha of 0.05 for all analyses.
  - 2.1. To test for differences between randomized groups for outcomes that are assessed multiple times (Aims 2a, 2b), our overall modeling approach will be the same as for Aim 1. That is, for each outcome, we will fit a fixed effects repeated measures model, where observations are modeled as nested within persons. Predictors included in the model will be GROUP, TIME, and the GROUP\*TIME interaction effect. However, for these secondary outcomes, the definitions of the TIME effect varies across these secondary outcomes, based on their assessment schedule. The distribution of the outcome variables also varies across these variables. Thus, we will implement this overall modeling approach for these variables as follows:

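### Outcome analyses are restricted to participants onboarded after unblinded randomisation, and no all-randomised analysis set is named

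*Combined protocol and SAP*

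**What the plan says.** Aim 1 (section II) is to "Test for differences between randomized groups on the primary outcome of this proof-of-concept RCT". Section IV gives the order of events: "After providing verbal consent, the participant is randomized. This is an unblinded study". Staff read the assignment from the randomisation sheet, "document this randomized assignment in our REDCap dataset, and will then onboard the participant", using a script of about 15 minutes. Allocation is by the rule "Randomization will be in a 1:1:1 ratio".

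Recruitment is counted at the later step: "We will stop enrollment when n=225 participants have been successfully onboarded to their randomized condition".

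The Analytic Plan (section VI) defines who is analysed: "All successfully enrolled participants (i.e., passed the screening process, was successfully onboarded to the assigned smoking cessation materials) will be included". For hypotheses that concern only SiS and QG, it explicitly admits only participants onboarded to those conditions.

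Neither the Analytic Plan nor any other section names an intention-to-treat or all-randomised set, or a sensitivity analysis in one. No section says what happens to someone who is randomised but not onboarded, and successful onboarding is not defined.

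**The concern.** Onboarding to the assigned materials can happen only once the assignment is known to both staff and participant. Membership of the analysis set therefore depends on an event that follows allocation and may be influenced by it. Randomisation protects the comparison of everyone allocated. It does not protect the comparison of those who passed a later step.

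Failure could plausibly differ by arm. SiS and QG require installing an app, whereas in the TAU arm "study staff will use an onboarding script to lead TAU participants through the NCI booklet". Section V lists inability to install the app as an example of a reason for which the PI may remove a participant, and that reason has no obvious counterpart in the booklet arm. Linking it to failed onboarding is an inference, because the documents do not make the connection.

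The stopping rule works in the same direction. A randomised participant who is not onboarded does not count towards 225, so recruitment continues past that person. The Week 6 primary contrast and the three-group secondary contrasts are the ones exposed.

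**Working it through.** **Inputs from the documents (sections IV and VI).** 64 per group at end of treatment, d = 0.50, 85% retention, 75 per group enrolled, 225 in total, 1:1:1 allocation, stop at 225 onboarded, pairwise tests only after the three-group test rejects at 0.05.

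**Assumptions.** The documents give no onboarding failure rate. Let q be the share of each app arm not onboarded (2%, 5%, 10%), with no failures in TAU. Let δ be the mean of those kept minus the mean of those left out (0.25, 0.5, 1.0 SD, either sign). Tests are two-sided, which the plan does not state.

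**1. The plan's own figure.** For a two-sample t test at d = 0.50 and two-sided 0.05, the noncentral t gives power 0.795 at 63 per group and 0.801 at 64. So 64 reproduces with a target of 80%, which is also not stated. Then 64/0.85 = 75.3, against 75 in the plan. The sample size is not in dispute.

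**2. Shift from leaving out the non-onboarded.** The mean of all randomised is (1 − q) × kept + q × excluded, so the mean of those kept exceeds it by q × δ.

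| q | δ = 0.25 | δ = 0.5 | δ = 1.0 |
|---|---|---|---|
| 2% | 0.005 | 0.010 | 0.020 |
| 5% | 0.0125 | 0.025 | 0.050 |
| 10% | 0.025 | 0.050 | 0.100 |

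**3. Error rates with no true effect, 64 per arm, both app arms shifted by s.** The three-group test follows a noncentral F with 2 and 189 degrees of freedom and noncentrality 64 × (2/3)s². This treats Week 6 as a single cross-sectional comparison, as an approximation to the contrast from the mixed model. The pairwise results come from 2,000,000 simulated trials with pooled variance, testing pairs at 0.05 only when the three-group test rejected.

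| s (SD) | Three-group test | One given app vs TAU | At least one app vs TAU |
|---|---|---|---|
| 0 | 0.050 | 0.0250 | 0.0416 |
| 0.005 | 0.0501 | 0.0251 | 0.0417 |
| 0.025 | 0.0520 | 0.0265 | 0.0437 |
| 0.05 | 0.0580 | 0.0309 | 0.0499 |
| 0.10 | 0.0830 | 0.0494 | 0.0759 |

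Because both apps shift equally here, the SiS-QG difference is itself unbiased. Its rejection rate moves only from 0.025 to 0.026 at 0.05 SD and 0.028 at 0.10 SD.

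**4. What an all-randomised analysis would cost.** With equal allocation and 225 onboarded in total, randomised per arm is N = 225/(1 + 2(1 − q)), and the number not onboarded is 2Nq. If everyone answers Week 6 at 85% and the non-onboarded gain nothing, there are 0.85N evaluable per arm and the effect becomes 0.5(1 − q). Power is for one two-sided t test at 0.05, ignoring the requirement that the three-group test reject first.

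| q | N per arm | Total randomised | Not onboarded | Evaluable per arm | d | Power |
|---|---|---|---|---|---|---|
| 2% | 76.0 | 228 | 3.0 | 64.6 | 0.490 | 0.789 |
| 5% | 77.6 | 233 | 7.8 | 65.9 | 0.475 | 0.773 |
| 10% | 80.4 | 241 | 16.1 | 68.3 | 0.450 | 0.742 |

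The reference is 0.801 at 64 per arm with d = 0.50.

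**5. How much of the shift is removed.** If the non-onboarded answer at rate r, their share among app-arm responders is f = rq/(0.85(1 − q) + rq), and the share of the shift that remains is (q − f)/q. For example, q = 5% and r = 0.50 give f = 0.025/(0.8075 + 0.025) = 0.030, so about 40% remains. For q = 2%, 5% and 10%, the remaining share is 0.41, 0.40 and 0.39 at r = 0.50, and 0.70, 0.70 and 0.68 at r = 0.25. It is zero at r = 0.85 and the whole shift at r = 0. This assumes that response within each subgroup is unrelated to outcome, and it ignores any help from baseline data in the model. At r = 0, power at d = 0.50 is 0.801, 0.803 and 0.806.

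**The case against.** The case against acting has real substance.

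- **Wording.** For the three-group analyses the sentence is inclusive, and the word only is reserved for the SiS/QG hypotheses. But the parenthetical defines the included population by onboarding, and the stopping rule counts participants the same way. If the sponsor does intend to analyse everyone randomised, the text still needs changing.
- **Rarity.** Onboarding is staff-led and scripted and comes directly after randomisation. Eligibility requires an Android phone or iPhone. Section II reports that remote nationwide onboarding was feasible in Study 2. Nothing in the documents supports a rate as high as 10%. This stands, and it is why the bias is judged probably small.
- **Size.** Within the assumed range, one given app versus TAU never exceeds 0.05 under the plan's own testing sequence. At least one app versus TAU exceeds 0.05 only at the corner of 10% failure and a 1 SD difference. SiS versus QG is almost unaffected unless failure differs between the two apps. This also stands.
- **Kind of set.** Everyone onboarded is kept regardless of later use, so this is a modified intention-to-treat set and not a per-protocol one. That is true, but the condition follows a known allocation and is undefined, so its neutrality cannot be assumed.
- **Counts.** Assignment is recorded before onboarding, so failures by arm could be tabulated later. That makes reporting them easy, but the plan does not commit to it.

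**Conclusion.** The concern holds as a conditional one. The stated rule makes a comparison described as between randomised groups depend on an event after unblinded allocation, and that event can differ between the app and booklet arms. If every randomised participant is onboarded, the two sets coincide and nothing is lost.

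If some are not, the size and direction of any bias cannot be learned from the documents. The material distortion in the table appears only at the far corner of the assumed range. These figures rest on assumed failure rates and prognostic differences, no failure in TAU, and equal failure in the two apps.

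The restriction should be fixed. It is not a fatal flaw: the expected bias is small, but the plan gives no means of showing that it is small.

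**What to change.** 1. For all three-group comparisons, make all randomised participants, analysed as assigned, the primary analysis set. The baseline SEQ is already available for them, because the baseline survey is "administered prior to the quit day (online, as part of a screening test" and Table 1 lists the SEQ-12 at baseline. Their arm is recorded in REDCap before onboarding.
2. State that follow-up surveys go to randomised participants who were not onboarded, unless they withdraw. The documents are silent on this.
3. Define successful onboarding, and report the number and reasons for non-onboarding by arm.
4. Keep the onboarded set as a sensitivity analysis.
5. Aims 2c, 2d and 2f ask about the support or materials provided. State how a participant who never received them is handled.

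The stopping rule of 225 onboarded can stay.

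The cost is SAP wording plus about 3, 8 or 16 non-onboarded participants to survey at 2%, 5% or 10% app-arm failure. The drawback is dilution: power for one app versus TAU falls from 80% to about 79%, 77% or 74%. The change also removes bias only as far as these participants answer. If none do, power is unaffected but the bias largely remains, so the counts by arm are needed in any case.

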## VI. BIOSTATISTICAL ANALYSIS

**Statistical Power.** This is a proof-of-concept trial. Therefore, our primary endpoint is a process variable, a shorter-term variable that is linked to subsequent change on the outcome of ultimate interest. In this case, ultimately, the SiS app is hoped to have an effect on smoking cessation 6 months after the chosen quit day. Typically, effect sizes for mHealth interventions for smoking cessation are very small; their public health importance lies in their potential reach, where a small effect in a large population can make a considerable impact on public health. Specifically, for interventions delivered via websites, meta-analyses have reported an overall odds ratio for point prevalence abstinence of 1.14 [1.07-1.22], and Cohen's d=0.12. For text messaging, a Cochrane review estimated a relative risk of 1.54 [1.19-2.00] in favor of automated text messaging interventions compared to minimal smoking cessation support. Such effect sizes require large scale RCTs, which is beyond the scope of this proof-of-concept RCT. Thus, as a process indicator of subsequent smoking cessation, we have selected self-efficacy to abstain from smoking as our primary outcome variable, because self-efficacy has been identified as the primary mediator by which a text-messaging intervention conferred smoking cessation benefit. Similar to our study, this trial used the "Clearing the Air" booklet as the control condition, and

showed that self-efficacy observed one month after the chosen quit day mediated group differences in smoking cessation at the 6-month follow-up.

In selecting the sample size for this proof-of-concept trial, we were guided by the effect observed in that text-messaging trial. Namely, in the text-messaging study, the observed group difference between treatment and control at 1 month post quit day on self-efficacy was  $d=0.66$ . Thus, we conservatively powered our proof-of-concept RCT to detect an effect size of  $d=0.50$ . Using SAS PROC POWER, we calculated that we would need a sample size of  $n=64$  per group to detect an effect of  $d\geq0.50$ . Assuming a retention rate of 85%, we would need to enroll  $n=75$  per group in order to retain  $n=64$  by end of treatment. Thus, the total number of participants to be enrolled into this trial is  $n=225$  (3 randomized groups \* 75 participants to be enrolled in each group = 225).

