    - 2.1.1. (Aim 2a) Self-reported 30-day point-prevalence abstinence: the dependent variable will be a binary outcome variable (1=self-reported abstinence for 30 days, 0=not), which will be modeled over three timepoints (i.e., 6, 12 and 24 weeks post quit) using PROC GENMOD, where a binomial distribution with logit link function will be specified. The GROUP effect will include all three groups (SiS vs. QG vs.

TAU), as this outcome will be assessed in all randomized groups. Contrast statements will be used to derive the test statistics for the GROUP comparisons at Weeks 6, 12 and 24, given the overall longitudinal model. These contrast statements will test the null hypothesis that SiS = QG = TAU at the tested timepoints (i.e., Weeks 6, 12 and 24). If this null hypothesis is rejected ( $p<0.05$ ), we will conduct pair-wise follow-up tests that compare the three possible pairwise comparisons (i.e., SiS vs. QG, SiS vs. TAU, and QG vs. TAU).

2.1.2. (Aim 2b) Self-reported past week cigarette reduction: first, we will calculate reductions in cigarette consumption by subtracting the number of cigarettes smoked in the week leading up to the baseline assessment, as measured in the baseline survey, from the number of cigarettes smoked in the week leading up to the 2, 6, 12, and 24 week assessments, as assessed in these respective surveys. The resulting change score will be the dependent variable in the fixed effects repeated measures model, which will be modeled over four timepoints (i.e., 2, 6, 12 and 24 weeks post quit). We anticipate that this dependent variable will be normally distributed, but will also consider other possible distributions (e.g., Poisson). If normally distributed, this model will be fit in SAS using the PROC MIXED procedure. Contrast statements will be used to derive the test statistics for the GROUP comparisons at Weeks 2, 6, 12 and 24, given the overall longitudinal model. These contrast statements will test the null hypothesis that SiS = QG = TAU at the tested timepoints (i.e., Weeks 2, 6, 12 and 24). If this null hypothesis is rejected ( $p<0.05$ ), we will conduct pair-wise follow-up tests that compare the three possible pairwise comparisons (i.e., SiS vs. QG, SiS vs. TAU, and QG vs. TAU).

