- 2.2. To test for differences between randomized groups for outcomes that are only assessed at end of treatment (Aims 2c – 2l), for each outcome, we will use a fixed effects model, where GROUP is the only predictor, and score at end of treatment is the dependent variable. Histograms will be used to guide selection of the most appropriate distribution. We anticipate that we will use the normal distribution for the CSQ-8 (Aim 2c), use of strategies (Aim 2e), perceived impact (Aim 2f), the AS (Aim 2g), actual app usage (Aim 2h), self-reported app usage (Aim 2i), likeability of the app (Aim 2j), satisfaction with the app (Aim 2k), and the SUS (Aim 2l), as implemented via the PROC MIXED procedure in SAS. We anticipate that we will use the Poisson distribution for time spent applying content (Aim 2d), as implemented via the PROC GENMOD procedure in SAS. If the GROUP effect is statistically significant ( $p<0.05$ ), we will conduct pair-wise follow-up tests that compare the three possible pairwise comparisons (i.e., SiS vs. QG, SiS vs. TAU, and QG vs. TAU). These follow-up analyses will not be necessary for secondary outcomes that are only assessed for the SiS and QG conditions (i.e., Aims 2j-2l).
3. Exploratory mediational models (Aim 3): We will use mediational modeling, using the product-of-coefficients approach and a fully lagged model to test if hypothesized within-person changes (see Figure 1) occur, and if they are linked to subsequent abstinence. The independent variable will be randomized group assignment (i.e., SiS vs. TAU), and the outcome variable will be self-reported 30-day point prevalence abstinence as measured at 6-month follow-up). The mediators will be our theorized mechanisms of change, as listed in the Aim 3 (i.e., self-efficacy, emotional well-being, desire to smoke, breadth of thought-action-repertoire, processing of processing of self-relevant health information.). Baseline values on these constructs will be included in the model to control for individual differences

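### The primary Week 6 contrast is valid but makes almost no use of baseline SEQ, so it gives up precision and carries part of any chance baseline imbalance

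*Combined protocol and SAP*

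**What the plan says.** Section VI, Analytic Plan, item 1 specifies a repeated measures model in PROC MIXED with GROUP, "TIME (i.e., BL, Week 2, Week 6, Week 12 and Week 24") and GROUP*TIME as predictors. The primary test is then defined: "A contrast statement will be used to derive the test statistic for the GROUP comparison at Week 6, our primary endpoint". Its null hypothesis is equality of the three arms at that visit, and pairwise tests follow only if it is rejected at 0.05. The model has no baseline covariate and no constraint on the baseline means, and the contrast is not written as a change from baseline.

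Table 1 (section V) lists the "Smoking Self-Efficacy Questionnaire (SEQ-12") at baseline and at all four follow-ups. Section V places the baseline survey in screening, and section IV places randomisation after verbal consent on a later enrolment call.

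Other analyses in section VI do bring baseline in. Item 2.1.2 (Aim 2b) forms a change score by "subtracting the number of cigarettes smoked in the week leading up to the baseline assessment" from the follow-up counts. Item 3 (Aim 3) says: "Baseline values on these constructs will be included in the model to control for individual differences".

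**The concern.** Listing baseline as a level of TIME looks like baseline adjustment, but here it is not. Three arms by five visits gives 15 free cell means. One of these is a separate baseline mean for each arm, although randomisation makes the three true baseline means equal.

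Two things are at stake on the primary endpoint. First, if baseline SEQ predicts Week 6 SEQ even moderately, power is lost that could be had from data already collected. Second, if one arm happens to start higher, a fraction rho of that difference appears in the Week 6 estimate. The standard error allows for this on average over randomisations, but that does not settle the argument in the one trial where an imbalance is seen.

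**Working it through.** **Inputs from the documents.** d=0.50, 64 per group retained, 75 per group enrolled, 225 in total (section VI, Statistical Power); retention ("Assuming a retention rate of 85" percent); 1:1:1 allocation (section IV). **Assumed:** two-sided alpha 0.05 and 80% power for the plan's calculation; rho over a range; equal SDs (set to 1); dropout at random.

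**Reproducing the plan's figure.** A two-sample t-test with d=0.50 needs 63.8, so 64 per group, with 80.1% power at 64. 64/0.85 = 75.3, and 75 × 0.85 = 63.75. The plan's 64 and 75 are thus reproduced, as an unadjusted comparison with no baseline correlation.

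**Variance of the Week 6 contrast.** Take baseline and Week 6 only, with n0=75 and n6=64 per arm. The contribution of one arm to a between-arm difference is:

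- planned model (free baseline means): (1−ρ²)/64 + ρ²/75
- common baseline mean: (1−ρ²)/64

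The second is never larger. At ρ=0.5, planned = 0.75/64 + 0.25/75 = 0.01505, so SE = √(2 × 0.01505) = 0.1735. Common baseline = 0.75/64 = 0.01172, so SE = 0.1531.

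Pairwise power is Φ(0.50/SE − 1.96). The three-arm test is a 2-df test with noncentrality 0.125/(arm variance) for means 0.50/0.25/0. The middle value 0.25 is an assumption.

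| ρ | SE planned | SE common | Pairwise power planned → common | Three-arm test planned → common |
|---|---|---|---|---|
| 0.2 | 0.1763 | 0.1732 | 81.0% → 82.3% | 72.0% → 73.6% |
| 0.3 | 0.1756 | 0.1686 | 81.3% → 84.3% | 72.4% → 76.0% |
| 0.5 | 0.1735 | 0.1531 | 82.2% → 90.4% | 73.5% → 84.1% |
| 0.6 | 0.1720 | 0.1414 | 82.8% → 94.2% | 74.2% → 89.6% |

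At ρ=0.1 the pairwise gain is under 1 point (80.8% to 81.1%). The SE falls by 4%, 12% and 18% at ρ 0.3, 0.5 and 0.6.

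**Check with all three arms and five visits.** Generalised least squares under compound symmetry gives the planned contrast zero weight on baseline with complete data, and variance equal to that of the raw difference. If dropouts have baseline only, the ratio of common-baseline to planned variance is 0.92 (ρ 0.3) and 0.78 (ρ 0.5), as in the table. If some dropouts also have Week 2, the ratios are almost the same. The two-visit simplification does not drive the result.

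**Chance imbalance.** The SD of a baseline difference between two arms of 75 is √(2/75) = 0.163, so the chance that a given pair differs by more than 0.2 SD is 22%. The planned estimate moves by ρ times the imbalance: 0.3 × 0.2 = 0.06 SD, or 0.5 × 0.2 = 0.10 SD. In simulation, the overall type I error of the planned pairwise test is about 5%. In trials where one arm starts more than 0.2 SD above the other, it is about 7% (ρ 0.3) or 9 to 10% (ρ 0.5), against about 5% with the common baseline mean. In the other 78% of trials the planned test runs below nominal, at about 4.5% (ρ 0.3) or 3.5% (ρ 0.5).

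**The case against.** The planned analysis is valid, and nothing in the documents contradicts it. Everything beyond that depends on an unknown rho. Baseline is taken at screening, at least about seven weeks before Week 6, with a quit attempt and the whole intervention in between, so rho could be low. At 0.2 to 0.3 the gain is only 1 to 3 points. The plan also describes d=0.50 as conservative against an observed 0.66. At 0.66, pairwise power goes from 96.4% to 97.5% (ρ 0.3) or 96.7% to 99.1% (ρ 0.5), so little is gained. The equally spaced middle arm is the least favourable pattern for the three-arm test. With the middle arm at either end, power goes from 84.6% to 87.5% (ρ 0.3) or 85.5% to 93.2% (ρ 0.5). The raised conditional error is offset by the error below nominal in balanced trials. Aim 2b uses a change score because its outcome is defined as a reduction, so it shows no inconsistency with Aim 1. Lastly, the trial is unblinded and the document is dated January 2022; if outcomes have been examined, changing the primary model is not a mere coding matter.

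These points are fair, and they limit the size of the claim. The imbalance argument is the same loss seen from another side (the ρ²/75 term), not a second one, and the comparison with Aims 2b and 3 is only supporting. But none of them is a reason to keep the free baseline means. The 0.66 comes from a text-messaging trial against the booklet and says nothing about SiS against QuitGuide. Under the stated assumptions the common-baseline variance is never the larger one.

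**Conclusion.** The concern holds, as an efficiency gap and not an error. The planned contrast is unbiased over randomisations, keeps its type I error, and has a sample size that suits an unadjusted comparison. It makes no use of baseline SEQ with complete data and very little with 15% loss. At d=0.50 the pairwise power given up is about 1 point at ρ 0.2, 3 at 0.3, 8 at 0.5 and 11 at 0.6, and slightly more for the three-arm test under the 0.50/0.25/0 pattern. These sizes rest on an assumed rho, equal SDs and dropout at random. The direction rests only on baseline being measured before randomisation, which the documents establish. The change should be made, but the trial does not fail without it.

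**What to change.** Keep baseline in the outcome vector, constrain it to one mean common to all arms, and allow GROUP effects only at Weeks 2, 6, 12 and 24. State an unstructured within-person covariance. Keep the Week 6 contrast as primary. Section II (Aim 1) says: "Two subscale scores are created by averaging items assessing internal vs. external stimuli, respectively". Apply the model to each SEQ score that is analysed, with that score's own baseline.

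Baseline as a covariate would give much the same precision, but it drops participants who have a baseline and no follow-up survey. That conflicts with the Analytic Plan's rule that all successfully enrolled participants "will be included in the outcome analyses".

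The cost is one sentence in the plan and a few lines of PROC MIXED code, with no new data and no change in sample size, endpoint or contrast. The documents do not say whether outcome data by arm have been examined. If they have not, record the change before they are. If they have, justify the change and report the planned model beside it.
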